## Research content

### 1. Research Objectives

**Main objectives:** 1) To construct a generative image model based on preoperative CT/MRI; 2) the treatment response was evaluated in the training cohort based on the virtual image images generated by the model, including: disease control rate (DCR) and objective response rate (ORR), and compared with the best treatment response images after real treatment; 3) predict the prognosis of patients based on real pre-treatment imaging images (CT/MRI/DSA) and virtual post-treatment images, including progression-free survival (PFS) and overall survival (OS);

**Secondary objectives:** 1) Integrate text information such as patient demographic data, laboratory examination data, and image reports/surgical records to achieve cross-modal fusion and further improve the performance of the model; 2) Adopt machine learning methods based on causal inference to realize the recommendation of diagnosis and treatment plans.

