## 2) Validity:

Overall survival (OS) is defined as the time from the start of chemotherapy combined with immunotherapy to the patient's death from any cause, measured in "months". For subjects who were still alive at the time of data analysis, OS was calculated based on the date on which the subjects were last known to be alive;

Progression-free survival (PFS): defined as the time from the start of chemotherapy combined with immunotherapy to the first disease progression or death from any cause.

To assess response to treatment in patients with intrahepatic lesions:

- a. Objective response rate (ORR): according to RECIST 1.1 criteria, objective response rate = (CR + PR / CR + PR + SD+PD); Participants with CR + PR efficacy should be retested 4 weeks after the first evaluation.
- b. Disease control rate (DCR): according to RECIST 1.1 criteria, lesion control rate = (CR + PR + SD/ CR + PR + SD + PD); Subjects with CR + PR + SD efficacy should be retested 4 weeks after the first evaluation.

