### **3. Research Methodology**

This study is based on a multicenter retrospective cohort including a prospective test cohort to include patients with unresectable hepatocellular carcinoma who have received TACE in combination with target-immune therapy. The data comes from the clinical diagnosis and treatment records of 8 tertiary hospitals from 2016 to 2025, and strictly follows the preset inclusion standards.

Generative model construction: diffusion model-based treatment response simulator: input data: enhanced CT/MRI images at the patient's baseline, real post-treatment enhanced CT/MRI images and clinical features (Child-Pugh score, AFP level, treatment plan, etc.). Model architecture: The conditional diffusion model was used to dynamically simulate the virtual follow-up images of the best response after treatment with the treatment protocol (TACE embolic agent dose + target immune drug combination) as the generation conditions. Training mechanism: The model is optimized by comparing the differences in deep visual features between the generated images and the real follow-up images to ensure that the generated results conform to the laws of biological evolution. Quantitatively evaluate the visual fidelity of the generated images (FID index <25); The clinical rationality was scored by 3 interventional radiology experts by blind (on a 5-point scale  $\geq$  4 points were considered qualified).

Dynamic survival prediction framework: Capture 256-dimensional semantic feature vectors from the generated virtual images to characterize the dynamic changes of tumor microenvironment. The depth features extracted by the generative model are fused with the patient's clinical variables, and the key predictors are automatically identified through the gated attention mechanism. Survival risk modeling: Construct a Transformer-based time-series survival model to output individualized survival curves and survival probability predictions at key time points (12/24/36 months).

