Treatment decision support systems: causal effects deduction: quantifying the expected survival benefit of different treatment regimens (eg, TACE + lenvatinib + pembrolizumab versus TACE + bevacizumab + atezolizumab) using a counterfactual analysis framework. Generate a heat map of treatment regimen comparisons to visualize simulated tumor regression differences. Decision rule: When the median survival benefit of a regimen is expected to be more than 3 months and the confidence probability is greater than 80%, the system preferentially recommends the regimen.

Model validation strategy: Stratified by study center, randomly assigned to the training set (70%), validation set (30%), and multiple test sets.

Survival prediction assessment: main indicators: C-index evaluation of overall survival prediction

accuracy; Secondary indicators: 12/24/36 months of time dependence on AUC to assess discriminant ability at a specific time point; Calibration analysis: The Brier score quantifies the prediction error, and the calibration curve evaluates the risk prediction consistency. Comparative experimental design: baseline model (clinical variables only); benchmark model + real follow-up images; Datum model + generate model virtual image.

Reproducibility & Ethics: The model code and preprocessing process are published in the public repository (GitHub). The self-service resampling method (1000 times) was used to calculate the 95% confidence interval.

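### No stated image criterion tests whether a patient's virtual image matches that patient's own response; FID and cohort ORR/DCR can agree while per-patient agreement is at chance.

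*Protocol*

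**What the plan says.** Three parts of the Protocol assess the virtual images directly.

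- **Fidelity** (3. Research Methodology): "Quantitatively evaluate the visual fidelity of the generated images (FID index <25".
- **Plausibility** (same section): "The clinical rationality was scored by 3 interventional radiology experts by blind", with 4 or more on a 5-point scale counting as qualified. What the experts are shown, for example whether they see the baseline scan, is not stated.
- **Response** (1. Research Objectives, main objective 2): "the treatment response was evaluated in the training cohort based on the virtual image images generated by the model". The measures and comparator are "disease control rate (DCR) and objective response rate (ORR), and compared with the best treatment response images after real treatment". Section (6) Evaluation Indicators, under 2) Validity, defines both measures as proportions of the cohort, for example "objective response rate = (CR + PR / CR + PR + SD+PD".

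Two further elements, both in 3. Research Methodology, use individual data but are not image acceptance criteria.

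- **Training target:** "The model is optimized by comparing the differences in deep visual features between the generated images and the real follow-up images".
- **Survival-model comparison:** "baseline model (clinical variables only); benchmark model + real follow-up images; Datum model + generate model virtual image", with the C-index for overall survival as the main measure.

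The key indicators in section (6) (C-index, time-dependent AUC, calibration with Brier score, decision curves, Nagelkerke R²) all assess the prediction model, not the images.

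**The concern.** The study's claim is about individuals. A virtual image generated before treatment is meant to show how this patient will respond, and then to feed an individual survival curve, a regimen comparison and a recommendation (2. The entry point and significance of this study; 3. Research Methodology).

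The stated image measures answer other questions. FID is a distance between two sets of images, with no pairing of patients. The expert score asks whether an image looks clinically reasonable. ORR and DCR summarise a cohort. Good results on all of these would not show that a given patient's virtual image carries that patient's response.

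The location of the response comparison adds to this. It is placed in the training cohort, and the generator is optimised against real follow-up images. Even a patient-by-patient comparison made there could reflect fit to the training data rather than prediction.

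At stake is main objective 2, and the credibility of any survival prediction or regimen comparison that treats the virtual image as an individual forecast.

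**Working it through.** The Protocol gives no figure on this point that can be reproduced; FID <25 and a score of at least 4 are thresholds. The check is therefore logical, with a small calculation and simulation.

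**Inputs**
- Response rate p = 0.30 to 0.40. This is an assumption. It borrows the background figure for significant response in section 1 of the project justification, which is not stated to be a RECIST ORR or this cohort's rate.
- Test case: each patient's virtual image is replaced by the real follow-up image of another patient chosen at random (a permutation of the cohort). This generator ignores the individual by construction.

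**Step 1: set-level and cohort-level measures.** A permutation leaves the set of images and the count in every response category unchanged. Hence:
- FID = 0, which is below 25.
- Virtual ORR − real ORR = 0, and likewise for DCR.

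**Step 2: per-patient measures.** With virtual and real response independent and both at rate p:
- Agreement = p² + (1 − p)²
- Chance-expected agreement is the same quantity, so kappa = 0
- Sensitivity for CR+PR = p; specificity = 1 − p

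| p | Agreement | Kappa | Sensitivity | Specificity |
|---|---|---|---|---|
| 0.30 | 0.09 + 0.49 = 0.58 | 0 | 0.30 | 0.70 |
| 0.35 | 0.1225 + 0.4225 = 0.545 | 0 | 0.35 | 0.65 |
| 0.40 | 0.16 + 0.36 = 0.52 | 0 | 0.40 | 0.60 |

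**Step 3: simulation** (assumed: 500 patients, 32 image features, 200 replicates, log hazard = 0.5 × clinical score − 0.7 × latent response).
- FID and ORR difference: 0 at both p = 0.30 and p = 0.40.
- Mean agreement: 0.58 and 0.52. Mean kappa: −0.0006 and 0.004.

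**Step 4: would the survival-model comparison notice?** In the same simulation the C-index was about:
- 0.62 with clinical variables only;
- 0.71 with true follow-up information added;
- 0.57 with shuffled images given the weight of the true ones, and 0.62 with them weighted at zero.

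Shuffled images therefore bring no gain, and that comparison would show it. The C-index values depend on the assumed effects. The zero FID, zero ORR difference and chance kappa do not.

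**Step 5: what the survival-model comparison cannot separate.** The three models are clinical variables only, the same plus real follow-up images, and the same plus virtual images. None is clinical variables plus the baseline image. A virtual image is generated from the baseline scan, so it can carry baseline prognostic information. If the third model beats the first, the comparison cannot say whether the gain comes from a correctly predicted response or from the baseline scan.

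**The case against.** A reader might infer that every check in the plan is group-level, and that a generator ignoring the patient would pass them all. The Protocol does not support that reading, for these reasons.

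- **The survival-model comparison uses each patient's own outcome.** Step 4 shows that uninformative images would bring no gain in C-index. This stands. The check remains indirect: it has no threshold and lacks a baseline-image reference.
- **Objective 2 does not exclude pairing.** Its comparator is real images, "compared with the best treatment response images after real treatment", and ORR and DCR are built from per-patient RECIST categories. It would go too far to say that the objective only compares two percentages. The choice of agreement statistic may also be left to a statistical analysis plan, which was not available here. What the Protocol does fix is the pair of named measures, which are rates, and the cohort, which is the training cohort.
- **No success rule is stated for objective 2.** A reader might infer that FID below 25, good expert scores and equal ORR would together meet it. The Protocol says no such thing. FID and the expert score appear under model construction and are already described there as visual fidelity and clinical rationality.
- **The experts may see the baseline scan.** If so, a gross anatomical mismatch could fail. A generator that preserves anatomy but draws a generic response could still look reasonable.
- **The design conditions on each patient's baseline images, clinical features and treatment, and pairing in the training loss is implied.** This makes complete disregard of the individual less likely. A training loss is not a held-out check, however.

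It is also fair to say that the 52–58% follows from assuming independence. It shows what the stated measures cannot detect; it does not estimate how this generator will behave.

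**Conclusion.** The point holds in its limited form. No stated image criterion tests per-patient agreement between virtual and real response. FID and the expert score concern distribution and plausibility. The named response measures are cohort proportions, evaluated in patients whose real follow-up images train the generator. Agreement on FID, ORR and DCR is compatible with chance-level individual agreement: 52–58% with kappa 0, under an assumed response rate of 30–40% and no patient-level link. The kappa of 0 and the zero differences do not depend on the assumed rate.

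The survival-model comparison mitigates this in part but cannot attribute a gain to predicted response. The matter should be corrected because the validity of the images is a main objective. It does not show that the generator will fail, or that the study has no patient-level check at all.

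**What to change.** 1. In main objective 2, replace the training cohort with the held-out validation and test cohorts. If the validation set is used to tune the generator, the test cohorts should carry the result.
2. State that the comparison is paired by patient. Cross-tabulate virtual against real best RECIST category with kappa, and give sensitivity and specificity for CR+PR. Report the per-patient difference in target-lesion diameter with limits of agreement. ORR and DCR can stay as descriptive summaries.
3. State that FID and the expert score are image-quality checks only and are not evidence that response is predicted.
4. Add a clinical plus baseline-image reference model to the survival comparison, so that the contribution of the virtual image beyond the baseline scan can be seen.

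**Cost:** the virtual images of held-out patients must also be read for response, and one further model must be fitted. The result may look less favourable than matching rates would.

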## **5. The innovation of the project**

This study is a multicenter, retrospective, real-world study of unresectable hepatocellular carcinoma (HCC) undergoing TACE in combination with targeted immunotherapy in the project from January 2016 to June 2025. Baseline imaging data, previous treatments, adverse reactions, clinical outcomes, follow-up imaging data, longitudinal laboratory examination data, etc., were collected to construct a generative model and generate imaging images of the best efficacy after virtual treatment. Combine virtual and real pre-treatment images with other clinical information for accurate prognosis prediction.

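### The survival model in main objective 3 (real pre-treatment plus virtual image) is not among the three models the protocol compares, and the described framework names only the virtual image

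*Protocol*

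**What the plan says.** Two parts of the protocol name the real pre-treatment image as a direct input to the prognostic model. Main objective 3 (1. Research Objectives) is to "predict the prognosis of patients based on real pre-treatment imaging images (CT/MRI/DSA) and virtual post-treatment images", for both PFS and OS. Section 5, on innovation, restates it: "Combine virtual and real pre-treatment images with other clinical information for accurate prognosis prediction".

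Section 3, Research Methodology, describes the model to be built. Its survival framework will "Capture 256-dimensional semantic feature vectors from the generated virtual images to characterize the dynamic changes of tumor microenvironment". Then "The depth features extracted by the generative model are fused with the patient's clinical variables", and the last step is to "Construct a Transformer-based time-series survival model to output individualized survival curves". The baseline image appears in this section only as an input to the diffusion model: "input data: enhanced CT/MRI images at the patient's baseline, real post-treatment enhanced CT/MRI images and clinical features".

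The comparison, also in section 3, has three members: "baseline model (clinical variables only); benchmark model + real follow-up images; Datum model + generate model virtual image". The words baseline, benchmark and datum appear to be three translations of one clinical-variable model. The main indicator is the C-index for overall survival.

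**The concern.** The objective and the methods name different image inputs for the same model. An analyst who follows section 3 as written would report discrimination and calibration for clinical variables plus the virtual image, and those figures would then be read as the answer to main objective 3.

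Two things are at stake.

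- **The objective 3 model has no place in the comparison.** If baseline burden and change from baseline carry different prognostic weight, features of the post-treatment state alone may understate what the pair can do. The framework says its features describe change, yet it names only one end of that change as their source.
- **The contribution of the virtual image cannot be isolated.** The virtual image is generated from the baseline image. With no model holding clinical variables plus the real pre-treatment image, a gain of clinical plus virtual over clinical alone may reflect information already in the baseline scan.

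**Working it through.** **Step 1: inputs side by side.** The protocol ties no sample size, event count or target C-index to this point, so there is no stated figure to reproduce. The check compares the named inputs.

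| Place in the protocol | Clinical data | Real pre-treatment image | Virtual image | Real follow-up image |
|---|---|---|---|---|
| 1. Research Objectives, main objective 3 | not named here | yes | yes | no |
| 5. Innovation | yes | yes | yes | no |
| 3. Methodology, survival framework | yes | not named | yes | no |
| 3. Methodology, compared model 1 | yes | no | no | no |
| 3. Methodology, compared model 2 | yes | not named | no | yes |
| 3. Methodology, compared model 3 | yes | not named | yes | no |

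Compared models naming the real pre-treatment image: 0 of 3. Compared models naming the objective 3 pair: 0 of 3.

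**Step 2: modality.** Objective 3 lists CT, MRI and DSA. The generator inputs in section 3 are enhanced CT and MRI. DSA therefore enters no image pathway that the methods describe.

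**Step 3: how much could omitting the baseline image cost?** All effects here are assumed. Let B be baseline log burden (SD 1), D the log change (SD 0.5 to 1), with correlation 0 or -0.3 between them. Post-treatment burden is P = B + D. Survival is exponential with log hazard = a·B + b·D and no censoring. Compare the C-index of P alone with that of the full predictor a·B + b·D.

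| Assumed weights | C-index lost by using P alone |
|---|---|
| a = b | 0.000 |
| a = 0.5, b = 1 | 0.010 to 0.024 |
| a = 0.3, b = 1 | 0.025 to 0.049 |

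The largest loss occurs at SD(D) = 1, a = 0.3, b = 1, correlation -0.3: 0.670 against 0.719, a difference of 0.719 - 0.670 = 0.049. With the weights reversed (a = 1, b = 0.5) the loss is at most 0.024, so it does not require change to be the stronger predictor. When a = b, P carries everything and nothing is lost.

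**Step 4: allow for clinical variables.** Add one clinical proxy for baseline burden to P, over the eight settings with a = 0.5 or a = 0.3. The proxy is also an assumption, since the protocol does not list tumour size among its clinical features.

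| Correlation of proxy with B | C-index lost |
|---|---|
| 0.5 | 0.010 to 0.041 |
| 0.7 | 0.009 to 0.031 |
| 0.9 | 0.004 to 0.017 |

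**The case against.** The strongest reply is that section 3 is silent on the real pre-treatment image and does not exclude it. Nothing there says the virtual image is the sole image input. The fused features are described as coming from the generative model, which receives the baseline image, and a time-series survival model fits a baseline-plus-virtual sequence better than a single image. The comparison is in shorthand, in translated text.

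This limits how far the point goes. A reader might infer that the model uses the virtual image alone, that change from baseline is wholly absent, or that the objective 3 model will never be evaluated. The protocol does not support any of these. Clinical variables are fused in, and the planned image-report text (secondary objective 1) may carry baseline burden. The virtual image is built from the patient's own baseline scan, so some baseline information arrives indirectly. The Evaluation Indicators section applies its metrics to the prediction model without naming inputs, so the supported statement is that the objective 3 model is not among the three listed.

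The reply does not remove the discrepancy. If the pair is intended, section 3 does not say so, and the comparison describes its first model as clinical variables only. Nor is this detail left to an analysis plan: the protocol itself fixes the inputs and the comparison, and they do not match its main objective.

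The C-index figures are also open to challenge. They treat the change as perfectly known, whereas a virtual image only predicts it; they score the pair with the true weights; and they reduce an image to one number. That objection stands, so they are an upper range for their settings and not an expected loss.

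**Conclusion.** The inconsistency is real and lies in the current text. The objectives and innovation sections name the pair of images; the methodology names only virtual-image features with clinical variables, and 0 of 3 compared models contains the real pre-treatment image. Followed as written, the plan gives no listed comparison for main objective 3 and cannot show what the virtual image adds to the baseline scan it was generated from.

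The mismatch of inputs rests on the wording alone and needs no assumption. The size of any loss does: 0 to about 0.05 in C-index, illustrative, and lower if clinical variables carry baseline burden. It should be corrected before model building because it affects a main objective and is cheap to put right.

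**What to change.** Bring section 3 into line with main objective 3 and section 5.

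- Name the real pre-treatment image together with the virtual image as the survival model's image input, alongside clinical variables.
- Replace the comparison with four models, compared by C-index for overall survival: (1) clinical only; (2) clinical + real pre-treatment image; (3) clinical + real pre-treatment + virtual image; (4) clinical + real pre-treatment + real follow-up image.
- State that (3) against (2) is the contrast showing what the virtual image adds. Model (2) is essential: if the baseline image were added to the virtual and follow-up models without it, a gain due to the baseline scan could be credited to the virtual image.
- Keep clinical + virtual image, if wanted, as a labelled ablation.
- Reconcile DSA: either say where it enters the model or align objective 3 with the CT/MRI inputs in section 3.

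Baseline images are already to be collected, so the cost is mainly wording and one or two more models to fit. There are also more image features to regularise. If the second image were encoded at the same length (an assumption), there would be 256 + 256 = 512 image features before selection, which bears on the ten-events-per-predictor rule in the sample size section.

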(3) The models are mostly constructed based on the baseline status of patients, ignoring the dynamic changes of tumor burden and immune landscape in the treatment cycle, which is difficult to guide treatment adjustment in real time and does not meet the needs of precision medicine. Although the traditional longitudinal prediction model can incorporate dynamic changes, it needs to systematically collect follow-up data for multiple visits. In the real world, patient follow-up is often irregular, and there are medical referrals and referrals in other places, resulting in a large number of missing or uneven longitudinal imaging data, and it is difficult to align the information obtained at different time points and different devices. In addition, such models wait for patients to respond to treatment, which has a prediction lag. The LILAC system (Learning-based Inference of Longitudinal imAge Changes) represents an important breakthrough in this direction, which uses a self-supervised time-series deep learning algorithm to analyze small changes in a series of MRI scans to achieve dynamic monitoring of disease progression. The proof-of-concept study showed that LILAC was significantly superior to the traditional method in the prediction of embryonic development time sequence and geriatric cognitive score. In pediatric glioma studies, the time-series deep learning model improved the F1-score of 1-year recurrence prediction by 58.5% by analyzing serial postoperative MRI images, and the prediction performance increased with the increase of historical scans (plateau after 3-6 scans). However, the clinical translation of longitudinal models faces fundamental difficulties: patients with advanced HCC are often unable to complete the full process of imaging follow-up due to disease progression or adverse reactions, resulting in a lack of high-quality time series data; Data heterogeneity is caused by differences in image acquisition protocols in different centers. Ethics and privacy concerns limit multi-center data sharing. Therefore, there is an urgent need to develop new prediction paradigms that do not rely on real post-treatment images. Breakthroughs in Generative Artificial Intelligence provide a revolutionary solution to this.

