#### (2) Selection of research subjects:

This project is a real-world study, including retrospective training, validation and testing cohorts and prospective testing cohorts, all registries are derived from real cases in clinical practice, and the collected case data should include the following requirements:

1. Unresectable hepatocellular carcinoma confirmed by histopathological diagnosis and/or clinical diagnosis (typical imaging features, clinical manifestations, laboratory tests, etc.) (Annex: Guidelines for the diagnosis and treatment of primary liver cancer (2024 edition));
2. Patients who receive TACE combined with targeted immunotherapy on the basis of the diagnosis of unresectable hepatocellular carcinoma;
3. Liver function grade Child-Pugh A or B;
4. Over 18 years old, regardless of gender;
5. Expected survival time  $\geq$  3 months;
6. ECOG PS score  $\leq 2$ ;

7. Meet the following laboratory examination parameters;

- 1) Hematologic function: absolute neutrophil count  $\geq 1.0 \times 10^9 / \text{L}$ ; Platelet count  $\geq 50 \times 10^9 / \text{L}$ ; hemoglobin  $\geq 90 \text{ g/L}$ ; The international normalized ratio is less than 1.7 or the prothrombin time is prolonged by no more than 4 seconds,
- 2) Liver function: alanine aminotransferase/aspartate aminotransferase does not exceed 5 times the upper limit of normal; total bilirubin  $\leq 210 \text{ micromol/L} [\leq 2.38 \text{ mg/dL}]$ ; Albumin  $\geq 28 \text{ g/L}$ ,
- 3) Renal function: serum creatinine does not exceed 1.5 times the upper limit of normal.

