#### **(3) Sample size:**

Sample size estimation based on the core principles of predictive model development (TRIPOD statement). The core strategy follows an outcome event-driven approach, focusing on the number of target events (e.g., disease positivity). Using the method recommended by Riley et al., the minimum sample size was calculated by the R language pmsampsize package. The calculation parameters include: (1) expected model discrimination (e.g., AUC is preset to 0.8);(2) the estimated number of predictors in the final model (k according to the literature and pre-experiments); and (3) the expected effect strength of the predictor (conservative estimates). At the same time, considering the high-dimensional characteristics of radiomics, the total sample size meets the following empirical criteria: (1) the number of events  $\geq$  (10 times k (EPV principle); (2) Total sample size  $\geq$  (10 times k). The final sample size was increased by 10-20% to compensate for missing data and heterogeneity. Multicenter image heterogeneity was included in the sample size calculation, and the sample size adequacy was verified by Bootstrap sampling.

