**(4) Methods of extraction and allocation of research objects:**

All subjects in this study were derived from real cases in clinical practice.

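### The stated split does not secure a test in a hospital unseen during training, and its shares leave the source of the test sets undefined

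*Protocol*

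**What the plan says.** - **Allocation rule** (Protocol, section 3, Research Methodology, model validation strategy): "Stratified by study center, randomly assigned to the training set (70%), validation set (30%), and multiple test sets". No share is given for the test sets.
- **Data source** (same section): "The data comes from the clinical diagnosis and treatment records of 8 tertiary hospitals from 2016 to 2025".
- **Cohorts**: the section on selection of research subjects describes a study "including retrospective training, validation and testing cohorts and prospective testing cohorts". Section 3 says "This study is based on a multicenter retrospective cohort including a prospective test cohort". Neither says which hospitals supply which cohort.
- **Allocation section**: item (4), on extraction and allocation, gives no rule. It says only "All subjects in this study were derived from real cases in clinical practice".
- **Rationale** (section 1 of the project justification): it says that "the clinical translation of longitudinal models faces fundamental difficulties" and lists among them: "Data heterogeneity is caused by differences in image acquisition protocols in different centers".
- **Other mention of centre heterogeneity**: only in the sample size section, "Multicenter image heterogeneity was included in the sample size calculation, and the sample size adequacy was verified by Bootstrap sampling". It is not linked to validation.
- **Comparison to be made** (section 3): a clinical-variables model, that model plus real follow-up images, and that model plus generated images. The C-index for overall survival is the main indicator.

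**The concern.** A random split within each hospital puts the same scanners, contrast protocols and embolisation practice on both sides of the split. A deep image model can pick up features that identify the hospital. If survival also differs by hospital, those features predict survival in any test set drawn from the same hospitals, and they need not do so elsewhere.

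This bears on the main comparison. The image models could gain C-index over the clinical-only model by recognising the hospital, and test sets made up of the same hospitals could not separate that gain from information about the tumour. The bootstrap intervals do not help, because no resampling by centre is stated and resampling the same patients adds no new hospital.

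The intended product is a survival prediction and regimen recommendation system, so performance in a hospital that did not supply training data is what a future user needs to know. Eight hospitals make that question answerable, but the stated rule does not ensure that it is asked.

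**Working it through.** **Inputs.** From section 3 of the protocol: training 70%, validation 30%, test share not stated, 8 hospitals. Hospital sizes, total sample size and between-hospital survival or image differences are not given. Equal hospital sizes are assumed below.

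**Step 1: do the shares add up?** 0.70 + 0.30 = 1.00, so 1.00 − 1.00 = 0 remains for the test sets. The sentence cannot be carried out as one random split into three kinds of set.

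**Step 2: what could it mean?**

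- *Reading A: test sets are part of the same centre-stratified draw.* This is the plain grammar, since all three kinds of set follow one verb. The 70/30 must then apply to what is left after a test share t is removed: training = 0.70 × (1 − t), validation = 0.30 × (1 − t). For assumed values of t:

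| Test share t | Training | Validation |
|---|---|---|
| 10% | 63% | 27% |
| 20% | 56% | 24% |
| 30% | 49% | 21% |

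  For every t, each hospital contributes to each set, so hospitals unseen in training = 0 of 8.
- *Reading B: test sets lie outside the draw.* Training and validation still share hospitals. The test hospitals are not named, so the number unseen cannot be determined.

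Neither reading guarantees an unseen hospital.

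**Step 3: does another part of the text supply one?** The selection section names testing cohorts without hospitals. The allocation section has no rule. Centre heterogeneity appears only under sample size. The prospective cohort is introduced beside the eight-hospital data source with no separate source. It therefore appears to add a test over time, but its hospitals are not fixed.

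**Step 4: what would whole-hospital hold-out cost?** Holding out h of 8 equal hospitals gives a test share of h/8: 12.5% for one, 25% for two, 37.5% for three. For h = 2 with the 70/30 split kept in the other six:

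- training = 0.75 × 0.70 = 52.5%
- validation = 0.75 × 0.30 = 22.5%
- test = 25%

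A patient-level random test set with t = 25% gives exactly the same shares, so at equal test size hold-out costs no training patients. If the test patients were instead meant to come on top of the 70% and 30%, the training share would fall by 70 − 52.5 = 17.5 percentage points. Under leave-one-centre-out validation each of the 8 hospitals is unseen once, and each fit uses 7/8 = 87.5% of patients.

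**Step 5: size of the bias.** This cannot be computed. It depends on between-hospital survival differences and on how well images identify the hospital, and the protocol gives neither.

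**The case against.** The strongest reply is that the sentence is ambiguous and the concern settles it one way. Because 70% and 30% use up all patients, the test sets may sit outside the draw, and their plural could mean separate hospital cohorts. The prospective cohort's hospitals are open too. Text directly before the section on selection of research subjects was not available to this review and could define the cohorts. This stands. A reader might infer that the design cannot show performance across hospitals, or that 0 of 8 hospitals will be unseen at test. The document does not support either as settled fact: the first goes too far, and the second holds only under the literal reading.

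It can also be said that the rationale's remark concerns longitudinal models and is used to motivate an approach that does not need real post-treatment images. That is fair, so this is not a flat self-contradiction. The remark still bears on this model, which is trained on real baseline and follow-up CT or MRI and passes image features to the survival model.

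Finally, a centre-stratified random split is a legitimate internal validation, it keeps every hospital's image variety in training, and no visible text claims external validation. This also stands. It does not remove the need to say which hospitals supply the test sets. Nor is this a detail left open for the SAP: the protocol states the rule, and the rule as stated cannot be carried out.

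**Conclusion.** The point holds in a limited form. The visible plan has one allocation rule, its shares total 100%, and it reserves no hospital. Read literally it tests only in hospitals already seen; otherwise the source of the test sets is undefined. As written, a test in an unseen hospital is therefore not secured, and a gain of the image models over the clinical-only model could partly reflect hospital recognition. Whether it would, and by how much, is unknown.

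A reader might also infer that holding out two hospitals leaves training at about 70 to 75% of patients. It does not if the validation set is kept: the figure is 52.5% under equal hospital sizes.

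The conclusion rests on the visible text and on the prospective cohort coming from the same eight hospitals, which is likely but not stated. It is an inexpensive improvement worth making before modelling starts, not a flaw that invalidates the study.

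**What to change.** In the model validation strategy of section 3:

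1. Before any image is modelled, name about two whole hospitals as the retrospective test set, and use none of their patients for training or tuning of either the generative or the survival model.
2. Apply the centre-stratified 70/30 random split only to the remaining hospitals, and state that the shares refer to those hospitals.
3. State which hospitals supply the prospective test cohort and whether any of them also supplied training data.
4. Report C-index, time-dependent AUC and calibration separately for each held-out hospital, for all three models compared.

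Leave-one-centre-out validation of the survival model is an alternative. If the generative model is not refitted each time, the protocol should say so, because the left-out hospital's images would then have been used in training it.

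**Cost.** The change uses the same patients and needs new wording. The schedule places model construction from January 2026; once a test hospital's images have been used in training, the separation can be recovered only by retraining. Training sees six hospitals instead of eight, though the final model can be refitted on all. Per-hospital estimates will be less precise, and reported performance will probably be less favourable. Hospital sizes should be checked first, because unequal sizes would move the shares away from 52.5%, 22.5% and 25%.
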